What are the potential risks associated with each research procedure, intervention, evaluation and/or test? If data are available, estimate the probability that a given harm may occur and its potential reversibility.

The potential risks of standing are similar to general bouts of light physical activity, the most likely one being fatigue due to extended standing. The trials in which participants will be asked to maintain balance on a balance board run the risk of losing balance. Balancing on the balance board might pose additional risk of loosing balance and falling. We will cover all surface adjacent to the participant with thick styrofoam to prevent injury in the unlikely case of fall.

17. Risk Classification

What is the overall risk classification of the research?

- ◆ Minimal risk

Greater than minimal risk

18. Minimization of Risk

A. Describe how the subjects of the research will be monitored by the investigators and other research personnel to ensure their safety.

We will cover all surfaces adjacent to the participant with thick styrofoam to prevent injury in

the unlikely case of a fall when balancing on the balance board. Also, the study will be terminated if the participant report to have any kind of loss of balance while participating in the study.

B. Describe how the data collected will be monitored to ensure the safety of subjects. Identify who will perform the ongoing data and safety analysis, and describe the frequency of data analysis. If there is an independent Data and Safety Monitoring Board (DSMB) provide the charter, or describe (1) the composition of the DSMB membership, (2) the frequency of DSMB meetings and reports.

Collected data will be temporarily stored on an encrypted, password-protected local hard drive after data collection sessions have been completed. After being uploaded to a secure UNO Office365 server that only the listed personnel will have access to, they will be removed from the local hard drive. Hard paper copies will be stored in a lockable file cabinet within a locked room only accessible to the listed personnel. The PI will perform ongoing data and safety analysis. Data monitoring by the PI will occur every month.

C. Describe the auditing plan for research conducted. Identify who will conduct the audits and specify the audit frequency.

The primary investigator will be in charge of auditing the research (every 2 months) if discrepancies are found between the data collection, analysis, or logging procedures.

D. Describe the specific subject withdrawal criteria.

Participants will be asked throughout the data collection period if they are experiencing any physical discomfort and will be withdrawn from the study if stated that they do experience any physical discomfort. If the subject appears to be off balance or unsteady, they will be withdrawn from the study. Participants only need to express this to an investigator if they desire to withdraw. Suppose any aspect of the research negatively impacts their health or they no longer fit the eligibility criteria at any point in the research. In that case, the participant will be taken off the study. The study does not have any treatment or intervention beyond minimal physical activity. Therefore there is no consequence to the participant for withdrawing from the protocol

E. Describe the stopping rules for the research (e.g., the specific criteria for halting or early termination of the study).

The data collection sessions will be halted for reasons including, but not limited to: injury of any kind during data collection, equipment malfunction that may put the participants in increased harm, signs of physical injury, or expression of physical discomfort. We do not expect participants falling to be common during this project. However, if any participants fall, the study session will be terminated.

F. Describe plans and resources available to promptly address any subject injury.

The Biomechanics Research Building and the Health & Kinesiology Building have Emergency Action Plans that all investigators are familiar with. The procedures are listed in the attached document.

19. Potential Benefits to the Subject

Is there the prospect for direct benefit (eg, research on diagnosis or treatment of disease)?

No

20. Potential Benefits to Society

Describe the potential benefits to society that may reasonably be expected to result from this research.

The knowledge generated by this project will lay the foundations of a new way to understand suprapostural dexterity and its breakdown in various movement disorders.

FINANCIAL OBLIGATIONS AND COMPENSATION

22. Financial Obligations of the Subject

A. Who will pay for research procedures, interventions, evaluations and tests? Check all that apply.

Sponsor

Grant

CRC, CCTR

Costs or fees waived by Nebraska Medicine, UNMC- P, CHMC or CSP

♦ Department/Section funds

Other. Explain

B. Will any of the research procedures, interventions, evaluations and tests described above be charged to the Subject, the Subject's health insurance, or Medicare/Medicaid?

No

C. Are there any other financial obligations that the subject will incur as a result of participating in the study?

No

23. Compensation to the Subject for Participation

A. Will the subject receive any compensation for participation?

Yes

1. Describe the form of compensation, dollar amount (if applicable) and the prorated compensation plan (if applicable).

Participants will be compensated hourly at \$10 per hour for participation. Compensation will be prorated for the next full hour. For example, if the experiment lasted two hours and fifteen minutes, participants will be compensated for three hours. Participants will be compensated even if the study session is terminated prior to completion. Prorated compensation will be made regardless of whether withdrawal was voluntary (the participant decides to withdraw from the study) or involuntary (based on withdrawal criteria of the research protocol.)

At the end of the study session, using a laboratory computer, the participant will fill out and sign an online form with their payment details such as name, address, SSN, and citizenship status. None of these things will be recorded by the researcher. The form will then be sent to

the researcher to enter the amount the participant is to be paid and the cost center number for the grant the payment is to come from and submit for departmental approval. Once this is complete it will be sent to the accounting department of UNO for processing. A check will be sent to the participant at the address written on the form.

PRIOR REVIEW

24. Prior IRB Review

A. Has this study (or one substantially similar) been previously submitted to the UNMC IRB (or the Joint Pediatric IRB) and then withdrawn by the investigator for any reason?
No

B. To the best of your knowledge, has this study (or one substantially similar) been considered by another IRB and disapproved?

No

SUBJECT IDENTIFICATION & RECRUITMENT

25. Method of Subject Identification and Recruitment

A. Will prospective subjects learn about the research and then contact the investigator about participation (for example, in response to a print, electronic, radio or television advertisement; referral by a clinician or other specifically for this research)?

Yes

1. If so please describe how prospective subjects will become aware of the research

(for example, by a print, electronic, radio or television advertisement, or thru another mechanism)?

Healthy young adults will be identified and recruited by word of mouth and campus-wide email. Email lists provided by faculty or staff from departments within the University of Nebraska at Omaha will be used for the recruitment email.

2. Who will be responsible for receiving these inquiries from prospective subjects?

Primary and secondary investigators

3. Will prospective subjects be screened for eligibility prior to informed consent?

No

B. Will the investigator make the initial contact with the potential subject to tell him/her about the research (for example, by contacting existing or past previous patients or research participants; or by contacting prospective subjects thru school records, or thru support groups or other Interest Groups; or thru use of the Hospital Opt-In Database)?

No

C. Will this study be listed in the clinical trial registry at www.clinicaltrials.gov?

No

OBTAINMENT OF INFORMED CONSENT

26. Waiver or Alteration of Informed Consent

A. Is a complete waiver or alteration of consent requested?

No

27. Waiver of Signed Consent

Is a waiver to obtain signed consent requested?

No

29. Process of Informed Consent

A. When will the prospective subject/parent(s)/guardian(s)/LAR be approached relative to their/the subject's actual participation in the study?

Potential participants will be scheduled at their earliest convenience.

B. Where will informed consent be obtained, and how will the environment be conducive to discussion and thoughtful consideration?

Informed consent will be obtained in the Biomechanics Research Building on the University of Nebraska at Omaha campus. All consent will take place in one of our evaluation rooms, which are private, similar to a doctor's office. The investigator obtaining consent from the participant will explain all procedures verbally to the participant until they fully understand the risks, benefits, and protocol of the study and feel comfortable to begin the data collection.

C. Who will be involved in the process of consent and what are their responsibilities?

The PI, secondary investigators, and participating personnel will be permitted to consent to participants. All investigators will be responsible for clearly explaining the research study, including the benefits and risks of participation. They will minimize the possibility of coercion or undue influence, and no exculpatory language will be used to imply that the participant is waiving their legal rights.

D. Is there any limitation on the amount of time allotted to the process of consent?

No

E. How will the process of consent be structured for subjects who are likely to be more vulnerable to coercion or undue influence?

We are not recruiting potential participants who may be vulnerable to coercion or undue influence. If investigators suspect the participant may be vulnerable, the participant will not be allowed to participate in the research study.

F. Will non-English speaking subjects be enrolled in this research?

No

Provide justification for exclusion of non-English speaking subjects

A translator is not available to assist this project.

G. How will it be determined that the subject/parent(s)/guardian(s)/LAR understood the information presented?

We will assess participant comprehension using the second suggested method: asking the individual to describe the research in sufficient detail, whereby the subject demonstrates an acceptable level of comprehension of all elements of the consent form.

31. Information Purposely Withheld

Will any information be purposely withheld from the subject during the research or after completion of the research?

No

RESOURCES

33. Describe the resources available to safely conduct this study at each study sites specified in Section I.7.

The Biomechanics Research Building and the Health and Kinesiology Building have Emergency Action Plans that all research personnel is familiar with. All storage, equipment, and emergency first aid kits are located within the building and are adequate for human subjects research.

LITERATURE REVIEW

34. References

Provide a full listing of the key references cited in the background (Section II.3). The references should clearly support the stated purpose of the study.

<https://doi.org/10.1002/hbm.22861>

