Understanding this interactivity is thus paramount to developing novel rehabilitative interventions to prevent falls and improve the quality of life in pathological populations. This project integrates a customizable life-size Trail Making Test with posturography, whole-body movement tracking, and eye tracking, along with state-of-the-art cascade modeling and network analysis methods to assess functional coordination across the whole body. We will leverage causal network analyses of multiplicative interactions instrumental in previous studies of whole-body exploratory motor behavior but not yet utilized in studying suprapostural dexterity. Aim 1 will investigate how multiplicative interactions among movement-system components support suprapostural dexterity. We hypothesize that maintaining an upright stance would produce a functional network of multiplicative interactions among movement-system components. We also hypothesize that participating in the Trail Making Test would produce a succession of distinct, modular networks of multiplicative interactions among movement-system components. Aims 2 will investigate how multiplicative interactions among movement-system components support suprapostural dexterity in the face of postural instability. We hypothesize that destabilizing contact with the ground surface when maintaining an upright stance will produce modular networks of multiplicative interactions with increased connectivity among these modules compared to stable standing. We also hypothesize that destabilizing contact with the ground surface in the Trail Making Test would produce a succession of distinct, modular networks of multiplicative interactions with increased connectivity among these modules compared to stable standing. This modeling framework offers a new way to understand suprapostural dexterity and its breakdown in various movement disorders in light of recent theoretical developments in cascade modeling and network physiology.

PURPOSE OF THE STUDY AND BACKGROUND

2. Purpose of the Study

What are the specific scientific objectives of the research?

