A significant challenge of standard linear network models has been the discontinuity between one functional module and the next. The precision of cascade-driven network modeling will allow us to understand suprapostural dexterity without switching between different control modes. Cascade modeling allows us to articulate how seemingly differentiated forms can arise from similar fluid interactions across many timescales (Kelty-Stephen et al., 2022, 2013; Kelty-Stephen and Mangalam, 2022b). This capacity for cascades to extend across timescales appears similarly in postural sway, no matter whether we load the upper body (Furmanek et al., 2020; Kelty-Stephen et al., 2020), destabilize contact with the ground surface (Kelty-Stephen, 2018; Mangalam and Kelty-Stephen, 2021), or increase visual effort (Mangalam et al., 2021). Indeed, network modeling of cascade-like interactivity may reflect control parameters governing bodily coordination across the timescales of the fastest reflex to the slowest movement unfolding across the entire task. This modeling framework offers a new way to understand suprapostural dexterity in light of recent theoretical developments in cascade modeling and network physiology.

We will use network modeling of cascade-like interactivity as a fresh way to understand suprapostural dexterity in light of recent theoretical developments in cascade modeling and network physiology. The precision of cascade-driven network modeling will allow us to understand suprapostural dexterity without implying any discontinuity between one functional module and the next. Healthy adults will maintain an upright stance on a stable surface in one condition and perform the Trail Making Test while maintaining an upright stance in the other. We hypothesize that maintaining an upright stance would produce a functional network of multiplicative interactions among movement-system components (Hypothesis 1.1). The Trail Making Task has been shown to measure several capabilities

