such as cognitive flexibility, alternating attention, sequencing, visual search, and motor speed, among other functions (Bowie and Harvey, 2006; Reitan, 1958; Sanchez-Cubillo et al., 2009). Performing the Train Making Task must introduce longer-timescale constraints on the postural system already satisfying the shorter-timescale demands of postural stability. It is expected that the culmination of shorter-timescale postural constraints and longer-timescale constraints imposed by the Trail Making Task will produce more differentiated network configurations or modular networks. Accordingly, we hypothesize that taking part in the Trail Making Test would produce a succession of distinct, modular networks of multiplicative interactions among movement-system components (Hypothesis 1.2).

Aim 1 approach network modeling from the vantage point of traditional modeling that these modular networks should be static. In Aim 2, we will relax this premise to investigate how the cascade-like interactivity exhibits a continuum of variability within so-called modular networks and could underwrite the transitions between separate network configurations. Specifically, we will investigate how shorter-timescale perturbations destabilizing the upright stance interact with the longer-timescale constraints on task completion to facilitate transitions among different network configurations. We base our predictions on recent findings of functional brain networks, which suggest that performing two tasks simultaneously or in close succession relies on the flexible reconfiguration of the brain networks (Alavash et al., 2015; Ekman et al., 2012; Hilgetag et al., 2001; Lam and Shin, 1998). Indeed, performance in different concurrent tasks benefits from unique functional brain networks at various timescales: integration of local, intermediate, or global networks (Alavash et al., 2015). Furthermore, the inability of the brain networks to sustain two separate topological configurations at once, each supporting the performance in one of the dual-task components, causes moment-to-moment fluctuations in the dual-task behavior (Alavash et al., 2016). Accordingly, we will examine the extent of modularity and the strength of connectivity between modular networks on multiplicative interactions as part of Aim 2.

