Aim 2 is about unseating one of these modular networks with a perturbation and showing that the reorganization of these networks can be understood from the cascade-like interactivity across the body. Healthy adults will maintain an upright stance on an unstable surfacea balance boardin one condition and perform the Trail Making Test while maintaining an upright stance on the same unstable surface in the other. We hypothesize that destabilizing contact with the ground surface when maintaining an upright stance will produce modular networks of multiplicative interactions with increased connectivity among these modules compared to stable standing (Hypothesis 2.1). We hypothesize that destabilizing contact with the ground surface when taking part in the Trail Making Test would produce a succession of distinct, modular networks of multiplicative interactions with increased connectivity among these modules compared to stable standing (Hypothesis 2.2).

Since fewer modular networks typically exhibit sparser intra-modular and denser inter-modular connections, we expect an inverse correlation between modularity and between-module connectivity from a theoretical standpoint.

CHARACTERISTICS OF THE SUBJECT POPULATION

4. Accrual

A. Is this study conducted solely at sites under the oversight of the UNMC IRB (e.g. UNMC, Nebraska Medicine, CHMC, UNO)?

Yes

1. How many subjects will need to be consented (per group, as applicable) in order to achieve the scientific objectives of the research?

50 healthy adults; 25 men and 25 women

2. What is the statistical or other justification for the total number of subjects described above?

Sample size determination was made based on previously observed values of statistical descriptors of movement variability in older and younger adults (older: $H = 0.64 \pm 0.08$; younger: 0.76 ± 0.07 (Hunt et al., 2014; Kaipust et al., 2013; Raffalt et al., 2021; Vaz et al., 2019; Vaz et al., 2020) and the procedure outlined in Kuznetsov and Rhea (2017). The method entails generating simulated datasets with known parameters. Power Analysis conducted across 1000 simulated datasets revealed that 16 participants per group will yield 86%, 94%, and 100% power to detect a difference of 0.1, 0.05, and 0.3 in H for fixed effects of Sex and the two nestings of experimental manipulation. We will recruit $N = 25$ participants per age group to account for possible attrition, equipment failures, etc.

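### The power quoted for N = 50 concerns H, which the described analysis never uses, so it is not power for the connectivity contrasts in Hypotheses 2.1 and 2.2

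*Protocol*

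**What the plan says.** Item 4 (Accrual), A.1 gives 50 healthy adults, half men and half women. A.2 asks for the statistical or other justification. Its answer begins "Sample size determination was made based on previously observed values of statistical descriptors of movement variability in older and younger adults", with H of 0.64 ± 0.08 in older and 0.76 ± 0.07 in younger adults. It then reports, from 1000 simulated datasets, that "16 participants per group will yield 86%, 94%, and 100% power to detect a difference of 0.1, 0.05, and 0.3 in H". The sentence goes on to assign these figures to fixed effects of sex and of two nestings of the experimental manipulation. The step from 16 to 25 is explained as 25 "participants per age group to account for possible attrition, equipment failures, etc".

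The hypotheses are in item 3 (Background and Rationale). On the unstable surface, modular networks are expected with "increased connectivity among these modules compared to stable standing (Hypothesis 2.1") and, during the Trail Making Test, "increased connectivity among these modules compared to stable standing (Hypothesis 2.2").

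Item 12.C describes the analysis:
- displacement series for centre of pressure, centre of mass and markers;
- multifractal spectrum width, with a t-statistic against 32 surrogates;
- VAR networks built on that t-statistic and thresholded to binary form;
- an impulse-response regression at a 5% Type I error rate;
- module extraction;
- a comparison of inter- and intra-module connection strength across conditions.

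**The concern.** H appears only in the sample-size paragraph and is not defined there. The quantity that decides Hypotheses 2.1 and 2.2 is between-module connectivity, stable against unstable. The protocol gives no effect size, variance or detectable difference for it, and does not say that H stands in for it.

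What is at stake is how the results will be read. With 86% to 100% power as the only statistical support for N = 50, a null result on connectivity could be taken as coming from a well-powered study. The protocol does not show that it would be.

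**Working it through.** **Step 1: trace H through the protocol.**

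| Place | Quantity |
|---|---|
| Item 4, A.2 (power) | Difference in H; planning values from older and younger adults |
| Item 3, Hypotheses 2.1 and 2.2 | Between-module connectivity, unstable against stable |
| Item 12.C, multifractality | Spectrum width and surrogate t-statistic |
| Item 12.C, network modelling | VAR weights on the t-statistic, thresholded |
| Item 12.C, comparison of networks | Inter- and intra-module connection strength |

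No row after the first uses H, and no text converts a difference in H into a difference in any later row. In the reference list, the titles of the sources cited for H concern walking or gait variability, as does the title of the cited power procedure. This study measures standing, in one age range of 19 to 35 years (item 6).

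**Step 2: try to reproduce the stated power for H.** Inputs from A.2: n = 16 per group; differences 0.1, 0.05 and 0.3; SD 0.07 and 0.08 (assuming the ± values are SDs). Alpha is 5% (item 12.C); two-sided is assumed.

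Pooled SD = √((0.07² + 0.08²)/2) = 0.0752.
Power ≈ Φ(δ/(SD·√(2/16)) − 1.96), with √(2/16) = 0.3536.
- δ = 0.1: 0.1/(0.0752 × 0.3536) = 3.76; Φ(1.80) = 96%.
- δ = 0.05: 0.05/(0.0752 × 0.3536) = 1.88; Φ(−0.08) = 47%.

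| Difference in H | Stated | Normal approximation, SD 0.08 to 0.07 | Exact t, SD 0.08 to 0.07 |
|---|---|---|---|
| 0.1 | 86% | 94–98% | 93–97% |
| 0.05 | 94% | 42–52% | 40–50% |
| 0.3 | 100% | about 100% | about 100% |

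Only the 100% is reproduced. Solving SD = δ/((1.96 + z_power)·0.3536):
- 86% at 0.1 needs SD = 0.1/((1.96 + 1.08) × 0.3536) = 0.093.
- 94% at 0.05 needs SD = 0.05/((1.96 + 1.555) × 0.3536) = 0.040.

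No single SD gives both. A within-person test could explain part of this. With n = 16, SD 0.07 and an assumed correlation of 0.7, the SD of differences is 0.07·√(2 × 0.3) = 0.054, and paired power for 0.05 is 93%. With SD 0.08 it is 85%. The three figures may therefore belong to different effects, but the protocol does not say which figure goes with which effect or variance.

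**Step 3: what could be said about connectivity.** Power cannot be computed from the document. For illustration, assume one connectivity score per person and condition and a two-sided 5% paired t-test; the protocol states neither. Effects are in SDs of the within-person difference.

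| Completers | Detectable at 80% / 90% power | Power for 0.3 | Power for 0.5 |
|---|---|---|---|
| 50 | 0.40 / 0.47 | 55% | 93% |
| 32 (2 × 16) | 0.51 / 0.59 | 38% | 78% |

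The 32-completer row takes the groups to be the sexes and is the full reserve: 1 − 16/25 = 36% loss. The protocol does not predict a loss of that size.

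**Step 4: the group label.** The age-group wording in A.2 conflicts with the single age range in item 6 and with the split by sex in A.1. The total is unaffected: 60 weeks less 10, at one participant per week (A.3), is 50.

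**The case against.** The best defence has four parts.

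**The conditions were powered.** The sentence names the experimental manipulation as well as sex. A reader who stops at the older and younger planning values might infer an age comparison unrelated to the conditions, and the document does not support that. This stands, but the powered outcome is still H.

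**The protocol claims no power for connectivity.** The sentence says H, and A.2 allows a justification other than a statistical one. This is true, and it makes the fault one of mismatch and not of false statement. Even so, the figures are the only statistical support given for the sample size.

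**A substitute measure may have been unavoidable.** The abstract describes the network analyses as "instrumental in previous studies of whole-body exploratory motor behavior but not yet utilized in studying suprapostural dexterity", so variance estimates for connectivity may not exist. This also stands. It is a reason to state the limitation.

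**A separate analysis plan might use H or supply the link.** It might. But the protocol itself states both the sample-size basis and the network analysis, and the two do not meet.

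Two stronger readings should be resisted. One is that N = 50 is too small. The illustration does not show this, since an effect of 0.5 SD would have 93% power with 50 completers. The other is that the H figures are miscalculated. Step 2 shows only that two of them do not follow from the stated SDs in a simple two-sample test.

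**Conclusion.** The point holds in a limited form. The power of 86%, 94% and 100% concerns H, the described analysis does not use H, and nothing ties H to between-module connectivity. The figures are therefore not power for Hypotheses 2.1 and 2.2. This part rests on the text alone and needs no assumption.

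The size of any shortfall is unknown. Under the paired-test assumption, power with 50 completers is 55% for an effect of 0.3 SD and 93% for 0.5 SD. Whether it falls below or within the quoted range depends on an effect size that the protocol does not give.

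A reader might extend the point to Aim 1. The text does not support that: Hypotheses 1.1 and 1.2 say that a condition "would produce a functional network of multiplicative interactions among movement-system components (Hypothesis 1.1") or "would produce a succession of distinct, modular networks of multiplicative interactions among movement-system components (Hypothesis 1.2"). Neither states a contrast between conditions, so no power consequence follows.

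The age-group label is a minor wording error that A.1 already resolves. The sample-size paragraph should be corrected; the sample size need not change.

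**What to change.** Keep N = 50 and rewrite the paragraph in item 4, A.2:

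1. State that the quoted figures concern differences in H and are not power for the network hypotheses.
2. Keep 86%, 94% and 100% only if each is given with its effect (sex, or which nesting) and the between- or within-person variance used. Otherwise remove them.
3. Give N = 50 a basis in one of two ways. Either state the detectable stable-versus-unstable difference in between-module connectivity, with the per-person score, the test and the assumptions; or, if no variance estimate exists, describe 50 as a feasibility number. The values in step 3 of the working show the form such a statement could take and are not proposed as protocol text.
4. Replace the age-group label with per sex, to agree with A.1.

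The cost is one reworded paragraph, with no change to participants, procedures or sample size. The downside is that the stated power becomes less favourable, or is withdrawn for Aim 2 if the feasibility route is taken.
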